5.2.4. HMR 11-013 Clinical Study

The United Kingdom's Defence Science & Technology Laboratory sponsored a randomized, double-blind, placebo-controlled, crossover, dose-escalation study to assess the safety, tolerability, PK, and PD of physostigmine salicylate and hyoscine (scopolamine) hydrobromide by continuous, IV infusion in healthy volunteers conducted by Hammersmith Medicines

Research ([HMR, 2016](#)). Data relevant to scopolamine safety from this study are described as follows. The clinical investigation demonstrated a tolerable safety profile of scopolamine in healthy volunteers up to a total dose of 797.5 μ g given over 4 hours of continuous IV infusion. Doses of 1200 μ g given over 10 hours were associated with psychiatric treatment emergent adverse effects in 2 subjects and lead to withdrawal (disorientation in 1 subject, and hallucinations and confusional state in the other). The 6 male volunteers administered 797.5 μ g over 4 hours resulted in an average C_{max} of 1.4373 ng/mL and an average AUC_{∞} of 6.749 hr*ng/mL. All 6 volunteers (100%) displayed treatment emergent adverse effects of somnolence, dizziness, and dry mouth, 5/6 blurry vision, 4/6 headache, 3/6 mood, and 1/6 coordination abnormality.

Though not a perfect comparison, HMR IV infusion data were compared to the IM injection data presented in the report by Ketchum and colleagues ([1973](#)), patients tended to exhibit the same pattern of symptoms although the IM injections were more tolerable. In the HMR study, 50% of subjects in the group receiving 0.5945 mg over 4 hours had blurred vision, whereas the ED_{50} for blurred vision in the Ketchum study was a single IM dose of 0.7 mg. Also in the HMR study, reports of a confusional state were observed in 50% of the combined subjects who received either 1.0 mg or 1.2 mg over 10 hours, whereas the ED_{50} for general confusion in the Ketchum report was a single IM dose of 1.4 mg. In both cases, the dose in the HMR (IV) study is about 85% of the dose in the Ketchum (IM) study. The PK of scopolamine when administered as a single IM injection of 6 μ g/kg into the deltoids of 6 healthy volunteers was found to support this hypothesis. A 90% confidence interval for the C_{max} and AUC was determined based on this dose and scaled proportionally to estimate the exposures in the Ketchum report. From this, similar exposure estimates can be correlated to similar symptoms as the IV groups.

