Urine PK Samples ^e	X		0-4 h										4-12 h			12-24 h			
Blood PK Samples	X		X	X	X	X	X		X		X		X		X	X	X	X	
Safety Lab Tests																			X
Adverse Events	X		X	X	X		X	X	X	X		X		X	X	X	X		
Concomitant Medications	X		X	X	X		X	X	X	X		X		X	X	X	X		
Continuous Cardiovascular Monitoring	Begin		ECG (3-lead) and vital signs (blood pressure (5-15 min intervals), heart rate, respiration rate, and pulse oximetry)(see Section 11.1.2 for details)														End		

Error! Reference source not found. Abbreviated physical exam at pre-dose; brief neurological assessment at 1 hour post dosing (+30 min) to assess alertness, orientation, ability to follow commands and coordination (refer to Section 11.1.5 and footnote ^d below).

^b If the PI or designee determines a subject is incapable of providing valid responses on the VAS due to the neuropsychiatric effects of Scopolamine HBT, the reason(s) why the VAS assessment(s) could not be done will be documented by time point in the source.

^c BPRS will be performed at 6 (+ 2) hours post dose. The + 2-hour window is provided to allow the investigator some discretion should the assessment need to be delayed or cannot be performed. The timing may be dependent on the emergence and severity of neuropsychiatric symptoms. The reason(s) why the BPRS was delayed or could not be done will be documented in the source.

^d RASS will be employed as part of the brief neurological assessment at 1 hour post dosing (+30 min) to assess alertness/level of consciousness, and at other times if adverse events of agitation or sedation occur.

^e Record the time and estimated volume of individual voids from pre dose through 24 hours post dose. This information will assist in the assessment of urine output and hydration, and will subsequently be used to calculate the total volume of urine pooled for each PK collection interval. Refer to Section 9.1.1.3 for details.

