11.1.6. Neuropsychiatric/Behavioral/Cognitive Assessments

The SCID-5-CT (customized) ([First et al-2015](#)) will be administered by a psychologist at Day-1 as a screening tool to exclude any subjects with major DSM-5 Axis I or II disorders. Due to the nature of the assessment, the SCID should not be repeated during this study. Therefore, for any subject who receives the SCID on Day -1, but is subsequently designated an alternate and readmitted on another day, the initial SCID will serve as their assessment of record.

Other assessments of neuropsychiatric/behavioral symptoms will be performed by appropriately experienced and trained study staff using the C-SSRS ([Posner et al-2011](#)), BPRS (expanded version 4.0, 24 items) ([Ventura et al-1993](#)), and RASS ([Sessler et al-2002](#), [Ely et al-2003](#)). A psychiatrist will be available by phone to consult with the investigator throughout the study. At the investigator's request, the psychiatrist will come to the clinic to evaluate a subject.

The C-SSRS Baseline/Screening version will be administered by study staff at screening, and the C-SSRS Since Last Visit version will be administered at Day -1 and at follow-up on Day 8.

Scoring and analysis will be performed according to the Columbia-Suicide Severity Rating Scale Scoring and Data Analysis Guide. Study staff administering the C-SSRS will complete C-SSRS training.

The BPRS will be performed by a psychologist or trained clinician at screening, Day -1 (baseline), at 6 (+ 2) hours post dose (timing at the discretion of the investigator), 48 hours post dose (prior to discharge), and on Day 8. For BPRS items assessed over time (eg, items 1, 2, and 3), the period of assessment should be over the prior week, except for assessments performed at 6 and 48 hours post dose, which will be assessed since the prior assessment. The + 2-hour window for the 6-hour post-dose BPRS is intended to allow the investigator some discretion should the assessment need to be delayed. The timing may be dependent on the emergence and severity of neuropsychiatric symptoms. If the investigator determines a subject is incapable of providing valid responses during the + 2-hour window, the reason(s) why the BPRS was delayed or could not be done will be documented in the source documentation.

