6.6.3 Handling of Other Missing Data

Other than AE data, for which missing will be imputed as the most severe, missing values will not be imputed for statistical summaries or analysis. All planned analyses of non-AE data will be conducted using all available data, including for participants who withdraw, with the exception of data to be censored following administration of rescue medications (as detailed in 6.11). In the event of study termination, all available data will be used for analysis of cohorts with at least one participant receiving the study drug.

Unless indicated otherwise, summary statistics will be reported for observed data only, with the exception of the cases described below.

Partial or incomplete start/end dates of the AEs or concomitant medications will be imputed to help determine treatment-emergent adverse events and prior or concomitant medications.

For incomplete start dates, following imputation rules will be implemented:

- Missing day - Impute as the 1st of the month unless month is same as month of first dose of study drug then impute using the day of first dose date.
- Missing day and month – impute as 1st January unless year is the same as first dose date then impute using the day and month of first dose date.

- Completely missing – impute using the first dose date unless the end date suggests it could have started prior to this in which case impute as 1st January of the same year as the end date.

When imputing a start date, ensure that the new imputed date is sensible i.e. is prior or equal to the end date of the AE or medication.

For incomplete end dates following imputation rules will be implemented:

- Missing day - Impute as the last day of the month unless month and year are the same as the month and year of the end of study, then impute as the end of study date.
- Missing day and month – Impute as 31st December unless year is the same as the year of the end of study date then impute as the end of study date.

Completely Missing – need to look at whether the AE/medication is still ongoing before imputing a date and also when it started in relation to study drug. If the ongoing flag is not missing then assume that AE is still present / medication is still being taken (i.e. do not impute a date). If the AE/medication has stopped and start date is prior to first dose date then impute as the 1st dose date, if it started on or after first dose date then impute as the end of study date.

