6.11 EXTENT OF EXPOSURE AND TREATMENT COMPLIANCE

This is a single dose study where the treatment is given in a single IM injection. The study medication (active or placebo) will be prepared by the pharmacist in accordance with the Drug Preparation Manual. Therefore, exposure will be closely monitored, and treatment compliance is not a major risk.

In the event that rescue medications (physostigmine, atropine, diazepam or lorazepam) are administered, data for the participant will be analyzed according to the dosage of Scop HBT received for measures taken up to the administration of the rescue medication. Thereafter, participant data will be treated differently by endpoint. Data collected after administration of the rescue medication for the BPRS, DSST, and/or RASS will be censored in analyses, though presented descriptively. Adverse events, injection site VAS, and PK data will not be censored.

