6.14.6 Neuropsychiatric Scales

Descriptive statistics (mean, standard deviation, minimum, maximum, median) of scores on the neuropsychiatric status assessments (BPRS and C-SSRS) will be presented for each timepoint by dosing group (placebo, 0.005, 0.007, 0.011, 0.014, 0.021mg/kg).

As the RASS will only be used if general agitation or sedation are reported, the number of participants with RASS performed, the reason for performance of the RASS, the time since injection when the RASS was administered, the RASS score, the resulting action taken (e.g., rescue drug administered, resolved or unresolved) will be presented by dose group and overall.

Signal neuropsychiatric events defined as DLTs (BPRS ≥ 40 or item score ≥ 4 at 48-hour post-dose evaluation) or symptoms (e.g., delirium, paranoia, and/or hallucinations) defined as adverse events will be noted and the affected participants' BPRS, C-SSRS, and RASS (if applicable) scores will be presented at each time point in relation to the determination of the event.

Change in BPRS scores from baseline (when BPRS≤25) will be compared for each dose level to placebo. Each time-point will be modeled separately. Changes in BPRS scores will be compared between each dose and the placebo group using a Wald test of coefficients from ANOVA.

Change in C-SSRS scores at SD 8 (from a baseline of zero) will be assessed. The proportion of individuals having a change in score from zero will be compared for each drug dosage level to the placebo group using Fisher's exact test. Scores for all participants receiving active Scop HBT will be compared to those receiving placebo.

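### The 6-hour BPRS test uses observed scores only, so subjects too affected by drug to be rated drop out of it and its result can be biased toward no difference from placebo

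*Protocol*

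**What the plan says.** The BPRS is given at screening, Day -1, 6 (+2) hours, 48 hours and Day 8.

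- **Cause of a missing 6-hour score.** Protocol 11.1.6 says of the 6-hour rating: "The timing may be dependent on the emergence and severity of neuropsychiatric symptoms". It then covers the subject who cannot be rated at all: "If the investigator determines a subject is incapable of providing valid responses during the + 2-hour window", in which case "the reason(s) why the BPRS was delayed or could not be done will be documented in the source documentation". The footnote to Protocol Table 4 (section 7.2) agrees: "The + 2-hour window is provided to allow the investigator some discretion should the assessment need to be delayed or cannot be performed". No score, rank or category is assigned.
- **Missing-data rule.** SAP 6.6.3 imputes missing adverse event data as the most severe. For everything else, "missing values will not be imputed for statistical summaries or analysis", and all available data are used.
- **Test.** SAP 6.14.6 models each time point separately: "Changes in BPRS scores will be compared between each dose and the placebo group using a Wald test of coefficients from ANOVA". SAP 6.3 takes all placebo subjects as the comparator. Protocol 12.1.2 makes the alternative one-sided, for larger increases on active drug.
- **Rescue.** SAP 6.11 removes further scores: "Data collected after administration of the rescue medication for the BPRS, DSST, and/or RASS will be censored in analyses, though presented descriptively".

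Neither document gives a sensitivity analysis for BPRS scores missing because of drug effect.

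**The concern.** The plan itself names neuropsychiatric drug effect as a reason why the 6-hour score may be absent. A subject lost for that reason is likely to be on active drug and more affected than the subjects who could be rated. The test then compares pooled placebo with the active subjects well enough to answer. If those left out would have scored worse than those rated, the mean difference is biased toward zero, and more so as more subjects become unratable.

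The 6-hour rating is the only BPRS between baseline and 48 hours, and the earliest neuropsychiatric or cognitive endpoint that is tested (DSST is tested at 48 hours and Day 8, C-SSRS at Day 8). SAP 1 says that future dosing regimens will rest partly on the safety data from this study. A null 6-hour result at a high dose could be read there as tolerability.

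**Working it through.** **1. The plan's own figures.** Neither document gives an effect size, standard deviation or power for the BPRS test. The nearest design figure is in SAP 3.5: 1 − (1 − 0.235)^6 = 0.7996, which reproduces the stated 80% chance of at least one event in 6 active subjects. The Benjamini-Hochberg thresholds in SAP 6.8 also reproduce: 1/110 × 0.20 = 0.0018, up to 5/110 × 0.20 = 0.0091. Neither speaks to missing scores.

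**2. Inputs.** From the documents: 6 active per dose, 10 pooled placebo (5 cohorts × 2), one-sided 0.05. Assumed: k of 6 subjects at one dose are unratable; their change, had it been scored, has mean +14 and SD 5; placebo change is Poisson with mean 0.7; the other active subjects are either like placebo or mildly affected (mean +2).

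**3. Mean difference.**
- All scored, others like placebo: (k/6) × (14 − 0.7) = 2.2, 4.4 and 6.7 points for k = 1, 2, 3. As planned, with the k subjects dropped: 0.
- All scored, others at +2, k = 3: (3/6) × 14 + (3/6) × 2 − 0.7 = 7.3. As planned: 2 − 0.7 = 1.3.

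**4. Simulated power, two-group pooled-variance t-test.** The worst-rank column is a one-sided Wilcoxon test with unratable subjects ranked worst.

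| Unratable | Other active subjects | All scored | As planned | Worst rank |
|---|---|---|---|---|
| 1 of 6 | like placebo | 0.055 | 0.052 | 0.10 |
| 2 of 6 | like placebo | 0.78 | 0.06 | about 0.25 |
| 3 of 6 | like placebo | 0.99 | 0.06 | about 0.51 |
| 3 of 6 | mean +2 | 1.00 | 0.57 | 0.95 |

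With the others mildly affected, planned power lies between 0.57 and 0.68 across these cases.

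**5. Six-group ANOVA.** Here the residual variance is shared with the other four doses, which are given no effect. The affected subjects are shifted by +15, an assumption taken from 40 (the 48-hour BPRS total that counts as a nonextreme DLT) minus 25 (the baseline ceiling). The SD is 2, 3 or 5.

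| Unratable | All scored, SD 2 / 3 / 5 | As planned |
|---|---|---|
| 1 of 6 | 0.45 / 0.30 / 0.20 | about 0.05 |
| 2 of 6 | 0.96 / 0.81 / 0.49 | about 0.05 |
| 3 of 6 | 1.00 / 0.99 / 0.81 | about 0.05 |

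If the remaining subjects have a true effect of +1, +2 or +4 (SD 3) and 2 of 6 are dropped, planned power is 0.13, 0.29 or 0.72, against 0.91, 0.97 and nearly 1.00 with everyone scored.

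The two calculations differ at 1 of 6. In a two-group test a single extreme value inflates the variance estimate, so there is almost no power to lose; a shared residual dilutes that. Which is nearer depends on the equal- or unequal-variance branch of SAP 6.10. In both, the mean difference goes to zero if the others are unaffected.

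**6. Counts alone.** One-sided Fisher test of unratable subjects against 0 of 10 placebo: for 2 of 6, C(6,2)/C(16,2) = 15/120 = 0.125; for 3 of 6, C(6,3)/C(16,3) = 20/560 = 0.036. If all 6 at a dose are unratable, that dose has no 6-hour test.

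**The case against.** **Much of the signal is captured elsewhere.** Clinically significant symptoms are adverse events, graded with BPRS items where one applies (Protocol 11.1.6). Symptoms needing medication are DLTs (Protocol 7.6.1). SAP 6.6.1 requires a table and listing of missing points with cause. The 48-hour BPRS rates its time-referenced items since the previous assessment. SAP 6.1 addresses the objectives mainly by description, the 6-hour contrasts are 5 of 110 exploratory tests, and the DSMB uses no tests. All of this stands and limits the consequence. It does not correct the 6-hour mean or p-value. A subject who was unratable, untreated and recovered by 48 hours may meet neither neuropsychiatric DLT criterion.

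**Unratable is not always psychiatric.** Protocol 11.1.6 says that general agitation and sedation match no BPRS item and assigns them to the RASS. A merely sleepy subject ranked below one who is hallucinating would be wrongly ordered. This stands and shapes the fix.

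**Stronger readings that the documents do not support.** A reader might infer:
- That half of the top cohort will drop out. For general confusion Protocol 5.2.4 reports that the ED50 "was a single IM dose of 1.4 mg", and 0.021 mg/kg × 70 kg = 1.47 mg. But that dose spans 0.021 × 55 = 1.16 mg to 0.021 × 85 = 1.79 mg, and confusion at some time is not inability to be rated at 6 to 8 hours. The share unratable is unknown.
- That 6 hours is the peak of effect. Protocol 5.2.4 cites effect lags of 2.5 to 3.5 hours for some measures and serum peaks at 10 to 30 minutes after subcutaneous dosing. Neither makes 6 to 8 hours the peak.
- That the highest doses will look closest to placebo. That is possible, not predicted; if the rated subjects are also affected, a difference can still appear.

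**Conclusion.** The concern holds as a bias in one exploratory test. The plan ties missing 6-hour scores to drug effect, imputes nothing, and tests observed scores only, so the 6-hour mean difference and p-value can be pulled toward no difference at the higher doses. The direction assumes that unratable subjects are mostly on active drug and would have scored worse than those rated. Both are plausible but not stated in the documents.

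The size is conditional. With the others like placebo, 2 or 3 unratable of 6 reduce the test to about its type I error rate. With 1 of 6 the loss is negligible in a two-group test and 0.15 to 0.40 in the six-group ANOVA (0.20 to 0.05, up to 0.45 to 0.05). With mildly affected others, part of the power remains. A reader might conclude that the toxicity itself goes unseen; it does not, because these subjects still appear in the adverse event, DLT and missing-data outputs. The plan should be amended, but the protocol's ANOVA need not be replaced.

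**What to change.** Keep the Protocol 12.1.2 ANOVA. In SAP 6.14.6, before unblinding:

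1. Add a supporting 6-hour analysis: one-sided Wilcoxon rank-sum, each dose against pooled placebo. Rank two outcomes worse than every observed score: BPRS not done because of neuropsychiatric drug effect, and rescue medication given before the 6-hour BPRS. Without the second, subjects censored under SAP 6.11 would still be missing from the supporting analysis.
2. Report counts of each outcome by dose and placebo beside the ANOVA result, with sedation separated from other incapacity.
3. State that a null observed-score ANOVA is not evidence of no effect when any subject was unassessable.
4. State whether a BPRS done after 8 hours counts as the 6-hour value; the text leaves this open.

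**Cost.** SAP wording, a short program and one eCRF field. The field is needed because the reason is kept in source, whereas SAP 6.6.1 takes the cause of missingness from deviations and disposition. Specified before unblinding, this fits SAP 6.2 as an additional analysis. Making the rank test the main test would change a protocol-specified analysis and need a revised protocol with its approvals.

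**Limits.** The rank test gives no mean difference and recovers power only in part: about 0.25 at 2 of 6 and 0.51 at 3 of 6 when the others are unaffected. The counts by dose are worth having whatever the p-value.

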7.3.2. Blinding

This study is double blinded. The study drugs (active and placebo) are filled in amber vials with a 1.2-mL fill volume, are clear and colorless liquids, and labeling is identical. The pharmacist and/or pharmacy technician at the clinical site will fill syringes for each study subject on dosing days to maintain the blind of the study staff. However, once a subject has been dosed with Scopolamine HBT, Injection, the study staff, including the investigators, will likely become unblinded as the CNS effects of Scopolamine HBT will be evident in the subjects, especially at the higher concentrations. Nevertheless, every effort should be made to maintain the blind, even at the higher concentrations. Study participants who become unblinded will be encouraged to maintain the confidentiality of the blind from other study staff if possible, as well as other study participants.

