Mental health/behavioral symptoms, judged to be clinically significant, should be reported as AEs at whatever time point they may be observed. As part of the reporting process, if the AE corresponds to an item on the BPRS, the relevant item on the BPRS scale should be used for assessing the severity of the event. In addition, if AEs of general agitation or sedation are reported, since these do not correspond to a specific item on the BPRS, the RASS should be used by a physician, physician assistant, or nurse to assess severity (see [Appendix D](#)).

The DSST ([Strauss et al-2006](#)) will be administered by appropriately trained study staff at screening, baseline (Day -1), 48 hours post dose (Day 3), and Day 8 to detect any persistent cognitive effects. The screening time point is included to reduce practice effects between baseline and re-administrations thereafter. The DSST will not be used to determine eligibility.

Note: Alternates who are readmitted on another day will have the BPRS, C-SSRS, and DSST repeated.

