11.3.1. Severity Assessment

All AEs will be assessed for severity by an investigator. Inherent in this assessment is the medical and clinical consideration of all information surrounding the event including any medical intervention required. The *Common Terminology Criteria for Adverse Events (CTCAE)*, version 5.0 (November 27, 2017) is a descriptive terminology that will be utilized for grading all AEs, with the exception of injection site reactions, which will be graded using the Local Reaction to Injectable Product table from the FDA's *Guidance for Industry: Toxicity Grading*

Scale for Healthy Adult and Adolescent Volunteers Enrolled in Preventive Vaccine Clinical Trials (see [Appendix B](#)).

Both guidance documents provide a grading (severity) scale for each AE term. Each event will be assigned one of the following categories: mild (grade 1), moderate (grade 2), severe (grade 3), or potentially life threatening (grade 4).

All events (Grade 1 or higher) must be recorded, regardless of group assignment (treatment or placebo), suspected causal relationship or clinical significance (e.g., including those determined by the Investigator as non-clinically significant).

Refer to [Appendix A](#) for assessing the severity of pain, pruritus, tingling, and numbness at the injection site (subject rating using the VAS); [Appendix C](#) for severity of pain, tenderness, erythema, and induration at the injection site (assessed by a physician, physician assistant, or nurse); and [Appendix D](#) for assessing the severity of agitation and sedation (using the RASS). The following criteria may be used for any symptom not included in the grading scale.

Any Grade 4 (potentially life-threatening) or Grade 5 (fatal) AE must be reported as an SAE.

The eCRF for AEs will reflect only the highest severity for continuous days an event occurred.

Mild	Grade 1 Does not interfere with routine activities Minimal level of discomfort
Moderate	Grade 2 Interferes with routine activities Moderate level of discomfort
Severe	Grade 3 Unable to perform routine activities Significant level of discomfort
Potentially Life Threatening	Grade 4 Hospitalization or ER visit for potentially life-threatening event
Fatal	Grade 5 Death

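### Protocol 11.1.6 and 11.3.1 set conflicting recording thresholds for neuropsychiatric adverse events and, with SAP 5.1.3.1, conflicting severity scales that are not fully mapped to grades

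*Protocol*

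**What the plan says.** **Recording.** Protocol 11.1.6: "Mental health/behavioral symptoms, judged to be clinically significant, should be reported as AEs at whatever time point they may be observed". Protocol 11.3.1: "All events (Grade 1 or higher) must be recorded, regardless of group assignment (treatment or placebo), suspected causal relationship or clinical significance". The latter sentence goes on to include events that the investigator considers not clinically significant.

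**Grading.** Protocol 11.3.1 says of CTCAE version 5.0 that it "is a descriptive terminology that will be utilized for grading all AEs, with the exception of injection site reactions"; SAP 5.1.3.1 repeats the rule with the same single exception. Protocol 11.1.6 instead says that "if the AE corresponds to an item on the BPRS, the relevant item on the BPRS scale should be used for assessing the severity". For general agitation or sedation it adds: "since these do not correspond to a specific item on the BPRS, the RASS should be used by a physician, physician assistant, or nurse". Further on, 11.3.1 itself names Appendix D "for assessing the severity of agitation and sedation (using the RASS".

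**Blinding.** Protocol 7.3.2 expects that after dosing "the study staff, including the investigators, will likely become unblinded as the CNS effects of Scopolamine HBT will be evident".

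**The concern.** The occurrence and intensity of AEs is a safety endpoint (Protocol 7.1) under a primary objective (6.1). CNS effects are the toxicity to be expected. Protocol 5.3.1.2 describes drowsiness, euphoria, impaired memory and confusion as normal at 0.005 to 0.007 mg/kg, the doses of the first two cohorts. The events whose recording is in doubt are therefore likely from the start of the trial.

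A judgment of clinical significance is discretionary, and here it would be made by people who probably know the treatment. If it decides whether a mild CNS symptom becomes an AE, perceived treatment can shape the incidence table. The section that follows takes the opposite approach: under 11.1.7 every nonzero injection site VAS score is an AE. CNS and local events would then be counted on different footings.

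For severity, a BPRS item score or a RASS score is not a grade. Two people following different sections could grade the same event differently, and several planned outputs use the grade.

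**Working it through.** The check is mainly a comparison of text.

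| Question | Protocol 11.1.6 | Protocol 11.3.1 | SAP 5.1.3.1 |
|---|---|---|---|
| Which events are recorded? | Mental or behavioral symptoms judged clinically significant | Every Grade 1+ event, whatever its clinical significance; no neuropsychiatric exception | Not addressed |
| Scale if the event matches a BPRS item | BPRS item | CTCAE; BPRS not mentioned | CTCAE; BPRS not mentioned |
| Scale for agitation or sedation | RASS | CTCAE by the single-exception sentence, RASS by a later cross-reference | CTCAE; RASS not mentioned |
| Who assesses severity? | For RASS, a physician, physician assistant or nurse | An investigator | An investigator |
| BPRS or RASS to Grades 1-4 | No conversion | No conversion; functional criteria for symptoms outside the grading scale | No conversion |

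**Threshold.** If 11.3.1 governs, the qualifier in 11.1.6 does nothing. If the qualifier does something, it breaches 11.3.1. The text does not say which section prevails.

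**Scale.** For BPRS-item events, 11.1.6 conflicts with both 11.3.1 and the SAP. For agitation and sedation, the conflict lies inside 11.3.1, between its single-exception sentence and its own reference to the RASS. The only partial anchors are in Protocol 9.2.1, for rescue purposes: a BPRS score of 5 or more on five named items, and a RASS score of 3 or more, are called severe. Sedation scores have no anchor. Under 11.1.5 a 1-hour RASS score goes into the eCRF for Cohorts 3-5, but nothing says whether a score of -1 (drowsy) is an AE.

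**What depends on it.**
- Threshold: the TEAE counts in SAP 6.14.5, chiefly for mild CNS events.
- Scale: the maximum-severity table in SAP 6.14.5, and the upper bound for severe AEs in Protocol 12.1.2.
- Possibly the rule in 11.3.1 that a Grade 4 event is an SAE. By Table 6, one SAE that is not already a DLT and not unrelated halts dosing and enrollment.
- Possibly SAP 6.6.3, which imputes missing AE data as most severe, if a site enters a BPRS or RASS score and leaves the grade blank.

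**What does not.** Neuropsychiatric DLTs (Protocol 7.6.1.1 and 7.6.1.2) rest on seizure activity, need for and response to treatment, the 48-hour BPRS score, or specific signs. BPRS and DSST changes are measured on schedule and compared with placebo whether or not an AE is recorded.

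**Illustration for the severe-AE bound.** The two-sided 80% Clopper-Pearson upper limit for x events in n subjects is the 0.90 quantile of Beta(x+1, n-x). For x = 0 and n = 6 this is 1 - 0.10^(1/6) = 0.319, which reproduces the 0.32 in SAP 6.4. The other results, with SAP Table 8 values in brackets where the table has a matching entry:

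| Active subjects | 0 events | 1 | 2 | 3 |
|---|---|---|---|---|
| 6 | 0.319 (0.32) | 0.510 (0.51) | 0.667 (0.67) | 0.799 (0.80) |
| 9 | 0.226 | 0.368 (0.37) | 0.490 | 0.599 (0.60) |

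Moving one subject from not severe to severe raises the bound from 0.32 to 0.51 with 6 active subjects, and from 0.23 to 0.37 with 9. This assumes that the choice of scale moves a subject across the line; the documents give no rate for that.

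**The case against.** The best defense is that the sections can be obeyed together. Section 11.1.6 says that clinically significant symptoms should be reported; it does not say that others must not be. Section 11.3.1 says that all Grade 1+ events must be recorded. Under 9.1.1.3 subjects are observed and asked how they feel at 11 scheduled times from 5 minutes to 12 hours, and all AEs are to be documented. This stands in part: exclusion of minor symptoms is an inference from 11.1.6. But on this reading the qualifier has no function, and a site working from the section specific to these symptoms could reasonably apply it.

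Second, the RASS does not simply set the two sections against each other, because 11.3.1 also names it. That is correct. 11.3.1 also gives functional criteria for symptoms outside the grading scale, with Grade 4 tied to hospitalization or an emergency visit for a potentially life-threatening event. A RASS of +4 or -4 is therefore not automatically Grade 4, and seriousness has its own outcome criteria in 11.2.2. This narrows the gap but does not say which scale sets the grade.

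Third, SAP 6.4 bounds SAEs where Protocol 12.1.2 bounds severe AEs, and the SAP supersedes the protocol on analyses. The effect on the bound therefore belongs to the protocol's version.

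Fourth, likely unblinding is already disclosed, and the same staff judge severity and relatedness for every AE, so removing the qualifier does not remove that bias. True; it removes one avoidable step where the bias can act.

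Fifth, low-level symptoms may exist before dosing. Inclusion criterion 12 allows a BPRS total of up to 25. If each of the 24 items scores at least 1, the minimum is 24, so at most one item can score 2. The problem is small, but the fix should be limited to new or worsened symptoms.

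**Conclusion.** The contradiction on the recording threshold stands. So does the contradiction on the severity scale for BPRS-item events, together with the inconsistency inside 11.3.1 over the RASS and the lack of a full mapping to Grades 1-4. The change is worth making because it removes a discretionary filter from a primary safety endpoint.

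Three stronger conclusions that a reader might infer are not supported:

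- *Two rival AE counts.* SAP 6.14.5 plans one TEAE count. The threshold makes that count ambiguous; the scale affects the severity tabulation, not the number of events.
- *A threat to the neuropsychiatric DLT counts.* Those DLTs use neither the clinical-significance qualifier nor the CTCAE grade.
- *A size taken from the intravenous study in Protocol 5.2.4.* That section calls the comparison of infusion with IM injection imperfect and says that IM dosing was better tolerated, so its event rates do not size this problem.

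The point concerns neuropsychiatric events in up to 60 subjects, 45 of them active. How many events would be recorded or graded differently cannot be computed from the documents. The shift from 0.32 to 0.51 shows sensitivity to one reclassified subject and is not a forecast.

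**What to change.** 1. In Protocol 11.1.6, strike the clinical-significance qualifier, so that the 11.3.1 threshold governs new or worsened symptoms after dosing. This fits 11.4.1, under which a condition in the medical history becomes an AE only if it worsens.
2. Reconcile 11.1.6, 11.3.1 and SAP 5.1.3.1 on one source for the severity grade: the CTCAE grade for every neuropsychiatric AE, with the BPRS item or RASS score kept as a supporting field. If the sponsor prefers BPRS or RASS to set the grade, one complete conversion table belongs in both the protocol and the SAP.
3. State in 11.3.1 who assigns the grade when a nurse or physician assistant has scored the RASS.
4. If any cohort was recorded before the change, state in the report which threshold and scale the site applied to it.

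The cost is a wording amendment to both documents and more mild AE entries on the eCRF.
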